We subsequently performed several studies which suggest that spinal release of oxytocin represents the protective factor against chronic pain after childbirth. Intrathecal injection of the specific oxytocin receptor antagonist, atosiban, temporarily reverses the blockade of nerve injury induced hypersensitivity in the postpartum period in rats. Similarly, intracerebroventricular administration of the  $\alpha$ -adrenoceptor antagonist, phentolamine, which is known to block the effects of lactation on activation of oxytocin-containing neurons in the paraventricular nucleus (PVN) of the hypothalamus, also temporarily reverses the blockade of nerve injury induced hypersensitivity in the postpartum period in rats. Finally, protection against hypersensitivity from nerve injury is abruptly reversed when pups are separated from dams for 24 hr, and this is accompanied by a large decrease in oxytocin concentration in cerebrospinal fluid. Although we are currently performing more clinical and laboratory studies to further define this mechanism, these data suggest that spinal oxytocin receptor stimulation in the period immediately following delivery protects against the generation of injury-induced hypersensitivity and subsequent chronic pain.

We recently completed a Phase 1 safety study of intrathecal oxytocin and observed no serious adverse events over the dose range studied (5-150  $\mu$ g). One subject at the 150  $\mu$ g dose had transient subjective numbness in sacral dermatomes, but this was preceded by a vasovagal episode beginning just prior to spinal injection, and this did not occur in other subjects at this dose. There were no objective signs of motor or sensory dysfunction in any volunteer, and blood pressure, heart rate, sensorium, corrected QT interval and serum sodium were unaffected.

We anticipate that oxytocin will be effective after spinal injection in humans to acutely relieve chronic neuropathic pain. For these future studies, we will use a cross over, controlled and blinded study of intrathecal oxytocin in patients with neuropathic pain below the umbilicus, with primary outcome being visual analog score for pain and secondary outcomes being areas of increased pain sensation to a normally painful stimulus (hyperalgesia) and pain sensation to what previously was an innocuous stimulus (allodynia).

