### **RANDOMIZATION GROUPS**

A computer generated randomization will be used to determine the group for each subject. Subjects will be randomized to receive an intrathecal injection of the saline placebo or 100 µg oxytocin on the first study visit, with the other on the second.

**Study Visit 1:** The participant will report to the CTSI Clinical Research Unit (CRU) at least 3 days prior to study visit 2. The participant will review and sign the Informed Consent. After informed consent is adequately obtained, a detailed medical history will be obtained from the participant, female participants will have blood drawn and sent to the laboratory to determine pregnancy status. Participants will be trained to estimate pain quantitatively using a 2 cm^2 peltier controlled thermode (TSA®) applied to an area of normal skin outside the area of ongoing pain. Typically, the participant is exposed to temperatures between 38 and 51 C using a random staircase method.

During this training period, the participant's blood pressure, heart rate, and peripheral oxyhemoglobin saturation will be recorded. A 12 Lead electrocardiogram (ECG) will also be performed.

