### **Study Visit 2**

On the second visit, the participant will report to the CTSI CRU in the morning. A peripheral intravenous catheter will be inserted into a vein in an upper extremity and lactated Ringers solution infused at 1.5 ml/kg/hr for the duration of the study. After obtaining baseline measures the subject will be placed into a lateral position and one of the investigator physicians will insert a #25 or #27 Whitacre spinal needle in a lumbar interspace using a sterile technique. After obtaining clear, free-flow CSF, a 2 milliliter sample of CSF will be obtained and stored for future use under IRB Protocol: 00003383, the sample will be stored with a unique identifier.

Oxytocin, 100 µg in a 3 ml volume, diluted with sterile normal saline, or a 3 ml injection of sterile normal saline (placebo) will then be injected over 30 seconds. Oxytocin will be prepared by Med Solutions Compounding, Winston-Salem, NC for research study purposes only. The spinal needle will be removed and the volunteer placed supine with the head of the bed elevated for the next portion of the study. Ongoing pain, pain to 225 mN von Frey filament application in the area of hyperalgesia, and areas of hyperalgesia and allodynia will be determined at 30, 60, 90, 120, 180, and 240 min after spinal injection. Blood samples (5 ml) will be obtained at 10, 20, 40, and 75 min after spinal injection by aspiration from the indwelling catheter, plasma will be prepared from the samples and frozen for subsequent analysis for oxytocin content. If blood cannot be obtained from the catheter we will not collect samples.

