#### Completion of Day 2 Assessment

1. Vital signs are within 20% of those on admission to the CRU
2. He or she can ambulate without difficulty (no motor, balance affects).
3. Someone other than the subject will take the subject home (requirement for participation).
4. Subject promises to stay home where he or she can be contacted by telephone (requirement for participation).

We will instruct the subject to call us, providing beeper and telephone numbers of the research nurse and the investigators should he have any questions or problems. The research nurse will call the subject at 6 hours and 12 hours post-spinal study drug injection inquiring about any perceived problems.

Study Visit 3: Approximately 24 hours after the spinal oxytocin injection the subject will report to the CTSI CRU to have a blood sample drawn for a Basic Metabolic Panel to assess serum sodium levels.

Study Visit 4: At least one week after Study Visit 2 the subject will return to the CTSI CRU for intrathecal injection of the cross over study solution. All procedures will be the same as Study Visit 2.

Study Visit 5: Approximately 24 hours after the spinal oxytocin injection the subject will report to the CTSI CRU to have a blood sample drawn for a Basic Metabolic Panel to assess serum sodium levels.

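### No serum sodium is scheduled before the first intrathecal injection, and neither session has its own pre-injection value

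*Combined protocol and SAP*

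**What the plan says.** All references are to the combined protocol and SAP.

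- **Sodium measurement.** Under Completion of Day 2 Assessment, Visits 3 and 5 each exist "to have a blood sample drawn for a Basic Metabolic Panel to assess serum sodium levels". Both are timed in the same words: "Approximately 24 hours after the spinal oxytocin injection the subject will report to the CTSI CRU".
- **Screening (Study Visit 1).** The only blood test is for pregnancy: "female participants will have blood drawn and sent to the laboratory to determine pregnancy status". The visit also has a medical history and an ECG, and "the participant's blood pressure, heart rate, and peripheral oxyhemoglobin saturation will be recorded".
- **Injection days (Study Visit 2, repeated at Visit 4).** "After obtaining baseline measures the subject will be placed into a lateral position"; this section does not itemise those measures. The blood draws it lists all come later: "Blood samples (5 ml) will be obtained at 10, 20, 40, and 75 min after spinal injection by aspiration from the indwelling catheter". They are for oxytocin content.
- **Eligibility.** No inclusion or exclusion criterion mentions sodium. Exclusion 2 leaves conditions that raise risk to the investigator's judgement.
- **Earlier data (Background).** In the Phase 1 study, over 5-150 µg, "blood pressure, heart rate, sensorium, corrected QT interval and serum sodium were unaffected".
- **Analysis (Statistical Rationale).** Only pain is covered. No analysis of sodium is given.

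**The concern.** Sodium matters enough in this plan to justify two dedicated visits, yet it has no reference value from before dosing. Blood pressure and heart rate are handled differently: Safety and Monitoring has them measured before injection and judged as change from baseline.

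What is at stake is the reading of individual safety results while the trial runs. Under the Data Safety Monitoring Plan the investigator reviews data after each subject's treatment, and serious events are reported within 24 hours with the trial halted until feedback. A low Visit 3 sodium would be assessed with the treatment masked, no earlier value to compare, and the second injection still to come. It could be put down to the study drug when it was there all along, or the reverse. A patient with low sodium that nobody knows about would also be injected without anyone being able to see it.

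**Working it through.** The plan states no figure on this point, so the check is a reading of the schedule, a count, and an illustration of precision.

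**1. Is a pre-injection sodium implied anywhere?** The measures named before injection are ongoing pain, maps of allodynia and hyperalgesia, and von Frey pain (Methods), plus blood pressure, heart rate and oxygen saturation (Safety and Monitoring). The only sample taken before injection on the day is 2 ml of CSF, stored for other use. A sodium draw is therefore unspecified rather than expressly excluded, but nothing indicates one.

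**2. Which values exist before which exposure?** Inputs: 2 groups of 20 (Methods); Visit 3 about 1 day after Visit 2, and Visit 4 at least 7 days after Visit 2 (Completion of Day 2 Assessment).

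- 24-hour values planned: 40 × 2 = 80. With a same-session pre-injection value: 0.
- Patients with any sodium before the first injection: 0 of 40.
- Oxytocin-first: 20 patients with no sodium before oxytocin.
- Saline-first: 20 patients whose only earlier value is the post-saline one from Visit 3, at least about 7 − 1 = 6 days before the oxytocin injection.

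**3. What does the crossover already provide?** Each completer has one 24-hour value after saline and one after oxytocin. The 95% half-width for the mean paired difference is t(0.975, 39) × SD/√40, with t = 2.023. The documents give no SD for sodium, so these SDs of the within-patient difference are assumptions:

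| Assumed SD (mmol/L) | 95% half-width | Difference detectable, 80% power (paired t, two-sided 0.05) |
|---|---|---|
| 1.5 | 0.48 | 0.68 |
| 2 | 0.64 | 0.91 |
| 3 | 0.96 | 1.36 |
| 4 | 1.28 | 1.82 |

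The mean drug effect on sodium can be estimated without a pre-injection sample.

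**4. How should a pre-injection value be used?** Let ρ be the correlation between the within-patient difference (oxytocin minus saline) in pre-injection values and the same difference at 24 hours, with equal variances. Relative to the 24-hour contrast alone, change scores multiply the half-width by √(2(1 − ρ)). Covariate adjustment multiplies it by about √(1 − ρ²). For an assumed SD of 2 (half-width 0.64) and assumed values of ρ:

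| ρ | Change scores | Covariate |
|---|---|---|
| 0 | 0.64 × 1.41 = 0.90 | 0.64 × 1.00 = 0.64 |
| 0.5 | 0.64 × 1.00 = 0.64 | 0.64 × 0.87 = 0.55 |

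Change scores gain precision only if ρ exceeds 0.5, and the documents do not give ρ. Apart from one degree of freedom, the covariate does not lose precision.

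**The case against.** The strongest reply is that the design supplies its own control. Low sodium after both sessions points to a pre-existing state; low sodium after oxytocin alone points to the drug. The randomised comparison needs no baseline, and the saline session also controls for the Ringer's infusion and the procedure, which a pre-to-post change would not. A reader might infer from the missing baseline that a drug effect on sodium cannot be judged at all. The documents do not support that: for completers it can be judged, although one value per session leaves individual attribution uncertain.

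A reader might also infer that sodium is never known before any injection. That is too strong, since the Visit 3 panel precedes the Visit 4 injection. What every session lacks is its own pre-injection value.

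Other points count for the plan. Phase 1 found sodium unaffected over a range that includes the 100 µg used here. The history and exclusion 2 can catch known low sodium. The plan has no sodium rule for proceeding to Visit 4 and does not count sodium among its significant side effects, so misattribution is possible, not shown. Nor would a baseline alone tell a blinded investigator which solution caused a fall.

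These arguments limit the point but do not remove it. The comparison across sessions arrives only at Visit 5, too late for reading the Visit 3 result and of no help to a patient who stops after one injection. History cannot reveal a condition that nobody has recognised. A baseline under blinding would still separate a value that was already low from one that fell after the injection.

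The crossover defence also needs a post-saline panel. Visits 3 and 5 both refer to the oxytocin injection, although one of the two is saline. Staff blind to treatment could not apply a rule limited to oxytocin, so a panel after both sessions is the sensible reading, but the text should say so.

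**Conclusion.** The point holds as a gap in individual safety assessment. It is not a flaw in the group comparison and does not touch the primary outcome. None of the 40 patients has a sodium value before the first injection, and none of the 80 planned values has a same-session reference. Twenty patients have no value before oxytocin, and 20 have only a post-saline value at least about 6 days old. The number who would stop after one injection, and how often low sodium occurs, cannot be taken from the documents, so no size of harm is claimed.

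This rests on two assumptions: that the unitemised baseline measures include no metabolic panel, and that the 24-hour panel is drawn after both sessions. If the first is wrong, the remedy is only to write the panel into the schedule. If the second is wrong, the saline comparator is lost and the gap is much larger. As it stands, this is an inexpensive improvement worth making.

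**What to change.** 1. Add a Basic Metabolic Panel at catheter insertion at Visits 2 and 4, before the Ringer's infusion and the injection. Have the Visit 2 result available to the investigator before injecting, or draw that sample at Visit 1 instead. This adds a measurement only; no sodium limit or management rule is proposed here.
2. State the sodium analysis: the within-patient oxytocin-minus-saline contrast at 24 hours, with the pre-injection value as a covariate. Use the pre-injection value for individual safety review as well, and do not replace the contrast with raw change scores.
3. Reconcile the wording of Visits 3 and 5 with the crossover, so that a panel is clearly required after the saline session and after the oxytocin session.

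**Cost.** Two routine panels per patient, or three if a Visit 1 sample is added to both, with no extra visit or staff. A venepuncture is needed if the catheter does not yield blood, which the protocol allows may happen, or in men if a Visit 1 sample is taken. Waiting for the Visit 2 result may delay that session; a Visit 1 draw avoids this.

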## **RISKS**

Risks of spinal needle insertion include pain on insertion, local bruising or soreness, post-dural puncture headache, and permanent nerve injury. Participants in this study will be informed regarding these risks. Local anesthesia will be used to prevent pain on needle insertion, and a small (#25 or #27) Whitacre tip needle used to minimize local trauma and risk of headache. We routinely telephone all subjects daily for 5 days. Participants will also be contacted weekly for 1 month, then approximately 6 months after the study to inquire regarding local discomfort or headache. There is a risk (less than 1%) of developing a headache from the spinal needles. If a subject develops a headache that does not go away and is bothersome, offer to perform an epidural blood patch. This procedure is 95% effective in treating the headache. Rarely (5 out of 100 times) is a 2nd blood patch needed. Other risks of the epidural blood patch are the same as the spinal. The risk of paralysis, infection or nerve damage from a spinal procedure is extremely rare, less than one chance in 20,000. The numbing medicine that we put under your skin right before the spinal needle is inserted may cause you to have a brief period (about 5 seconds) of mild discomfort. We have had no local discomfort lasting more than 2 weeks and only 1 headache in 438 subjects that required epidural blood patch treatment.

Risks of intrathecal oxytocin include unforeseen toxicity. This drug will be studied under FDA oversight and approval. The safety of spinal oxytocin has been extensively examined in animals, with no evidence of any nerve damage or other lasting effects, the FDA has approved this investigational study for humans, nearly 1000 humans have received spinal oxytocin in China without reported problems, and we did not observe toxicity in the recently completed Phase 1 study and in a study of over 90 subjects undergoing hip replacement surgery at this institution. Although this all suggests that it is safe to administer oxytocin, the exact risks are unknown. We will monitor subjects for many theoretical problems such as level of sleepiness, changes in blood pressure, heart rate and breathing. We will treat any side effects that the subject may experience if the changes are enough to concern us.

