## **HUMAN SUBJECTS**

All studies in volunteers will be performed in the CRU, which includes monitoring and resuscitation equipment and trained nursing support staff, or in in-patient settings of the Wake Forest Baptist Medical Center. All studies will be approved by the IRB and written informed consent obtained. The Project Investigators have all performed similar studies in volunteers and patients. The purpose of the study and all risks will be discussed with each volunteer, and all questions will be answered prior to obtaining written informed consent. Risks to be discussed include discomfort with needle and catheter insertion, risk of postdural puncture headache and spinal needle insertion, and potential period of pain if the study drugs are ineffective. The most likely bothersome risk to volunteers will be that of headache from i.t. needle insertion. We will discuss options for headache treatment including oral caffeine and epidural blood patch at the time of original consent and again should a headache occur. These will be provided at no charge to the volunteer, paid for by departmental funds. All data acquired will remain confidential with no reference to individuals in publications.

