### **Previous Experience in the CRU**

These investigators have, under NIH grant GM48085, regularly performed intrathecal injection studies with novel drugs for intrathecal delivery in healthy volunteers and in patients since 1990. Drugs studied include clonidine, fentanyl, neostigmine, adenosine, ketorolac and oxytocin. In addition, we have studied drugs approved for intrathecal delivery (morphine and bupivacaine) in the CRU. The most common adverse effect from these studies has been mild, transient backache and headache. Persistent headache requiring blood patch has occurred in <1% of subjects, likely reflecting the use of very small gauge (#27), pencil point spinal needles. Drug related adverse effects have included hypotension and bradycardia (clonidine), nausea (fentanyl, neostigmine), mild respiratory depression (fentanyl), transient back and leg pain (adenosine) and one episode of hypotension and bradycardia consistent with a vaso-vagal response to injection (oxytocin). The IRB and FDA recognizes that there are potential risks to these studies and has supported performance of this research in the CRU with the presence of an anesthesiologist and nurse,

appropriate monitoring, intravenous access, and immediate access to appropriate drugs for treatment.

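### The RISKS section puts needle headache at less than 1% without restriction, but the protocol's own data support that figure only for headache needing a blood patch

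*Combined protocol and SAP*

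**What the plan says.** Three sections of the combined protocol and SAP bear on headache after spinal puncture.

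- **RISKS** gives a general figure: "There is a risk (less than 1%) of developing a headache from the spinal needles". The next sentence deals with some of those headaches: "If a subject develops a headache that does not go away and is bothersome, offer to perform an epidural blood patch". The paragraph ends with the group's own count, "only 1 headache in 438 subjects that required epidural blood patch treatment". Near its start it says "Participants in this study will be informed regarding these risks".
- **HUMAN SUBJECTS** ranks the risk: "The most likely bothersome risk to volunteers will be that of headache from i.t. needle insertion". It names oral caffeine as well as the blood patch as treatments to be discussed.
- **Previous Experience in the CRU** says "The most common adverse effect from these studies has been mild, transient backache and headache", and then "Persistent headache requiring blood patch has occurred in <1% of subjects", which it describes as "likely reflecting the use of very small gauge (#27), pencil point spinal needles". Drug-related effects are listed after this, as a separate group.

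Under METHODS and Study Visit 4, each participant is to have two intrathecal injections at least a week apart. The needle may be 25 or 27 gauge.

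**The concern.** The same bound, below 1%, is attached to two different events. In RISKS it covers headache from the needle in general. In Previous Experience in the CRU it covers only persistent headache that led to a blood patch. The second event is part of the first, so a bound that holds for the second need not hold for the first. The description of mild headache as part of the most common adverse effect suggests that it does not.

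What is at stake is the accuracy of a risk figure for the complication that the protocol itself expects to trouble participants most, in a section whose contents are to be passed on to them. The trial's estimates, power and analysis are not involved.

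**Working it through.** **Inputs.** From RISKS: an unrestricted bound of less than 1%, and 1 blood-patch headache in 438 subjects. From Previous Experience in the CRU: less than 1% for blood-patch headache, and headache within the most common adverse effect, with no rate. From METHODS and Study Visit 4: two punctures per participant.

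1. **Can the RISKS figure be reproduced?** No. The documents contain one headache count, and it is restricted to headaches that needed a patch. No count or rate of all needle headaches appears anywhere.

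2. **What does the count support?** The proportion is 1/438 = 0.00228, or 0.23%. The exact (Clopper-Pearson) 95% limits are the 0.025 quantile of Beta(1, 438), which is 0.000058 (0.006%), and the 0.975 quantile of Beta(2, 437), which is 0.01265 (1.27%). The observed 0.23% agrees with the rate below 1% in Previous Experience in the CRU, so for blood-patch headache the two sections are consistent. The upper limit of 1.27% does not contradict a statement about what was observed. It means only that, as a prediction, a risk below 1% is not assured by this count even for the narrower event.

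3. **Which event does the RISKS sentence cover?** Its next sentence picks out headaches that persist and are bothersome, and offers the patch for those. The general figure is thus written for a wider set than the patched headaches. The mention of caffeine in HUMAN SUBJECTS likewise allows for headaches managed without a patch.

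4. **Is less than 1% plausible for the wider set?** Suppose the bound applied to the same 438 subjects (an assumption). Then 0.01 × 438 = 4.38, so at most 4 of them could have had any needle headache, including the one patched. That is hard to reconcile with headache forming part of the most common adverse effect. It is an argument from plausibility, because the ranking comes without a rate.

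5. **Per puncture or per participant?** RISKS does not say. If 1% were a per-puncture risk and punctures were independent (an assumption), two punctures would give 1 − (1 − 0.01)² = 0.0199, about 2.0% per participant. If it is already per participant over two punctures, no such step applies. The bound has no clear meaning for this crossover until the unit is stated.

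6. **Does past experience match this trial?** Previous Experience in the CRU credits its low blood-patch rate to 27-gauge needles, while this trial allows 25 or 27. This concerns only how far the past rate carries over; it is not a comment on the choice of needle.

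**The case against.** The strongest reply is that RISKS means post-dural puncture headache. That entity is named at the start of its paragraph, and again in HUMAN SUBJECTS and Long-term Follow-up. The mild headache in Previous Experience in the CRU could be a non-specific complaint gathered across studies of several drugs. Most common and most likely are rankings, not rates. On that reading both sections could be true. This possibility stands, and it is why the figure can be called probably too low but not shown to be wrong. It does not rescue the figure. The text never draws the distinction, it lists the mild headache apart from drug effects and moves straight on to needle gauge, and even post-dural puncture headache is a wider event than headache needing a patch, so the bound still has no count behind it.

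It is also fair to say that headache is disclosed, that treatment options are to be discussed before consent and again if a headache occurs, and that follow-up is daily for 5 days, weekly for 1 month and again at 6 months. The count of 1 in 438 is already correctly labelled. The fault is in one number, not in an omission of the risk.

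Three stronger readings are tempting, and the documents do not support them.

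- A reader might infer that participants are in fact given an understated risk. The consent form is not in the available documents, so what they are told cannot be checked.
- A reader might infer that headaches seen in the trial will be judged against the wrong expected rate. No section uses the figure as a benchmark, threshold or stopping criterion; the halt in the Data Safety Monitoring Plan is triggered by serious adverse events.
- A reader might double the upper limit for blood-patch headache to allow for two punctures. That needs one puncture per past subject and independence between punctures, and the documents state neither.

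**Conclusion.** The point holds as an inconsistency in a stated risk. The less-than-1% figure in RISKS is unqualified, while the protocol's data support it only for headache requiring a blood patch (1 of 438 = 0.23%, exact 95% CI 0.006% to 1.27%). For needle headache in general it is unsupported and probably too low. How much too low cannot be computed from the documents. The judgement of direction rests on reading the mild headache in Previous Experience in the CRU as at least partly due to the puncture, which the layout of that section favours but does not prove.

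No calculation in the protocol is wrong. This is a figure attached to too broad an event, and the efficacy design and analysis are unaffected.

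**What to change.** Reconcile RISKS, HUMAN SUBJECTS and Previous Experience in the CRU:

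- Label the less-than-1% figure as headache requiring a blood patch, with its basis (1 of 438, exact 95% CI 0.006% to 1.27%).
- Give the rate of any post-puncture headache separately, with numerator and denominator, from the group's existing records. If those records do not hold it, say that the rate is unknown and that mild headache is common.
- State for each figure whether it is per puncture or per participant, and that two punctures are planned.
- Check that the consent wording matches the corrected text.

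The cost is a wording change and a look through existing records. The downside for the sponsor is that the stated headache risk will probably look less favourable.
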